5.2 Dose Modification

Ibrutinib should be held or reduced in dose for toxicity or for concomitant use of CYP3A inhibitors (see Appendix A), as described in the sections below. Ibrutinib dosing adjustments are to be made according to the greatest degree of toxicity observed. Doses of ibrutinib which have been reduced for toxicity may not be re-escalated. All interruptions or changes to study drug administration must be recorded. If any patient discontinues study treatment or post-treatment observation, then the reason will be recorded.

Patients experiencing drug-related toxicities that are grade 1 or 2 according to CTCAE criteria should continue ibrutinib without dose modification. However the investigator may reduce the dose by one level if a grade 2 toxicity persists and significantly affects patient quality of life. If a patient experiences a CTCAE grade 3 or higher non-hematological toxicity, a grade 3 or higher neutropenia with infection or fever, or a grade 4 hematological event that is considered drug-related, ibrutinib should be held until resolution of toxicity to ≤ grade 1. Then the drug should be reinitiated at the starting dose. If the toxicity reoccurs, the dose should be reduced by one capsule (140 mg per day). A second reduction of dose by 140 mg may be considered as needed as per Table 5-2. If a patient experiences these drug-related toxicities despite two dose reductions, ibrutinib should be discontinued and the patient should be taken off the study. Patients should also be removed from study if off treatment for >3 weeks.

Recommended dose modifications for these toxicities are described below:

Table 5-2: Recommended dose modifications for ibrutinib

Toxicity occurrence	Dispensed As
First	Restart at 560 mg daily
Second	Restart at 420 mg daily
Third	Restart at 280 mg daily
Fourth	Discontinue Ibrutinib

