 - Grapefruit and Seville oranges should be avoided during ibrutinib treatment, as these contain moderate inhibitors of CYP3A (see Appendix A)
 - Co-administration of ibrutinib with strong CYP3A inducer, rifampin, in healthy subjects decrease ibrutinib plasma concentrations by approximately 10-fold. Avoid concomitant use of strong CYP3A inducers (eg, carbamazepine, rifampin, phenytoin, and St. John's Wort). Consider alternative agents with less CYP3A induction.
 - A list of common CYP3A inhibitors and inducers is provided in Appendix A. A comprehensive list of inhibitors, inducers, and substrates may be found at <http://medicine.iupui.edu/clinpharm/ddis/main-table/> This website is continually revised and should be checked frequently for updates.
- Anti-platelet Agents and Anticoagulants:
 - Warfarin or vitamin K antagonists should not be administered concomitantly with ibrutinib. Supplements such as fish oil and vitamin E preparations should be avoided. Use ibrutinib with caution in subjects requiring other anticoagulants or medications that inhibit platelet function. Subjects with congenital bleeding diathesis have not been studied. For guidance on ibrutinib and the use of anticoagulants during procedures/surgeries see Section 5.5.
 - Patients who need to be on anticoagulant therapy during treatment with ibrutinib should be treated with low molecular weight heparin as the preferred therapy. Patients who are on full dose anticoagulation therapy while being treated with ibrutinib and who experience concurrent grade 3 or 4 thrombocytopenia/bleeding despite single ibrutinib dose reduction will permanently discontinue ibrutinib treatment.
 - Subjects requiring the initiation of therapeutic anticoagulation therapy (eg, atrial fibrillation), consider the risks and benefits of continuing ibrutinib treatment. If therapeutic anticoagulation is clinically indicated, treatment with ibrutinib should be held and not be restarted until the subject is clinically stable and has no signs of bleeding. Subjects should be observed closely for signs and symptoms of bleeding. No dose reduction is required when study drug is restarted.

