9.2 Adverse Events of Special Interest (AESI)

Specific adverse events, or groups of adverse events, will be followed as part of standard safety monitoring activities. These events (regardless of seriousness) will be reported to Pharmacyclics Drug Safety per the SAE reporting timelines.

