9.2.1 Major Hemorrhage

Major hemorrhage is defined as any of the following:

- Any treatment-emergent hemorrhagic adverse events of Grade 3 or higher*. Any treatment-emergent serious adverse events of bleeding of any grade
- Any treatment-emergent central nervous system hemorrhage/hematoma of any grade

*All hemorrhagic events requiring transfusion of red blood cells should be reported as grade 3 or higher AE per CTCAE vX.X.

Events meeting the definition of major hemorrhage will be captured as an event of special interest according to Section 11.4.6 above.

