9.3.1 SAE Definition

An SAE is any adverse event, without regard to causality, that is life-threatening or that results in any of the following outcomes: death; in-patient hospitalization or prolongation of existing hospitalization; persistent or significant disability or incapacity; or a congenital anomaly or birth defect. Any other medical event that, in the medical judgment of the principal investigator, may jeopardize the subject or may require medical or surgical intervention to prevent one of the outcomes listed above is also considered an SAE. A planned medical or surgical procedure is not, in itself, an SAE. Also specifically excluded from this definition of SAE is any event judged by the principal investigator to

represent progression of the malignancy under study, unless it results in death within the SAE Reporting Period.

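### Section 5.2 has no bleeding exception to its grade 1-2 continue rule, so a low-grade bleed that Section 9.2.1 calls major hemorrhage has no required hold

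*Combined protocol and SAP*

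**What the plan says.** **Dosing (Section 5.2).** For low-grade toxicity the rule is "Patients experiencing drug-related toxicities that are grade 1 or 2 according to CTCAE criteria should continue ibrutinib without dose modification". One exception follows: "However the investigator may reduce the dose by one level if a grade 2 toxicity persists and significantly affects patient quality of life". A hold is required for drug-related non-hematological toxicity of grade 3 or higher, neutropenia of grade 3 or higher with infection or fever, and grade 4 hematological events.

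**Definition (Section 9.2.1).** Besides bleeds of grade 3 or higher, major hemorrhage includes two classes without regard to grade: "Any treatment-emergent serious adverse events of bleeding of any grade" and "Any treatment-emergent central nervous system hemorrhage/hematoma of any grade". A note narrows the low-grade set: "All hemorrhagic events requiring transfusion of red blood cells should be reported as grade 3 or higher AE".

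**Consequence (Section 9.2).** The only action attached to these events is reporting: "These events (regardless of seriousness) will be reported to Pharmacyclics Drug Safety per the SAE reporting timelines".

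**Seriousness (Section 9.3.1).** This is set by outcome, for example "in-patient hospitalization or prolongation of existing hospitalization", and not by grade.

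**Other bleeding-related dosing rules.** Section 5.3 deals with anticoagulation. When therapeutic anticoagulation has to be started, "treatment with ibrutinib should be held and not be restarted until the subject is clinically stable and has no signs of bleeding". A patient on full-dose anticoagulation stops permanently for grade 3-4 thrombocytopenia or bleeding that occurs despite a dose reduction. Section 5.5 requires holds around minor, major and emergency procedures.

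**The concern.** The protocol classifies bleeds in two ways that do not meet. For reporting, a serious or CNS bleed is major at any grade. For dosing, only the grade counts, and at grade 1-2 the instruction is to carry on. A patient admitted for a grade 2 gastrointestinal bleed, managed without red cells and without a procedure, is reported urgently as a major hemorrhage while the dosing section says to continue at the same dose.

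The stake is the safety of the individual patient. Section 1.3.3.4 says that major hemorrhage on ibrutinib has sometimes been fatal and names gastrointestinal and intracranial bleeding. Section 5.5.1 holds the drug for at least 3 days on each side of a needle biopsy because of the risk of bleeding, yet no hold is required for an actual low-grade serious bleed. The test of the primary endpoint is not at issue.

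**Working it through.** **Which events have no required hold.** The plan states no figure to reproduce, so the first step sets the sections side by side. A bleed is read here as a non-hematological toxicity.

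| Drug-related bleed | Major under 9.2.1? | Hold required? |
|---|---|---|
| Grade 3 or higher | Yes | Yes, Section 5.2 |
| Transfused with red cells | Yes, recorded as grade 3 or higher | Yes, Section 5.2 |
| Grade 1-2, serious or CNS, needing a procedure | Yes | Yes, Section 5.5.1, 5.5.2 or 5.5.3 |
| Grade 1-2, serious, not transfused, no procedure | Yes | None found |
| Grade 1-2, CNS, not transfused, no procedure | Yes | None found (Section 9.2.2 not seen) |
| Grade 1-2, neither serious nor CNS | No | None, and none is argued for |

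Rows four and five are the gap. By the protocol's own drafting they are not empty: if every serious or CNS bleed were grade 3 or higher, the two any-grade classes would add nothing to the first.

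**Whether another section closes it.** Sections 1.3.3.3 (diarrhea) and 1.3.3.5 (atrial fibrillation) refer the investigator to Section 5.2. The bleeding section, 1.3.3.4, refers only to Sections 5.3 and 5.5, which cover anticoagulation and procedures. Section 5.1 stops treatment for unacceptable toxicity. Section 5.4 stops it at the investigator's discretion or when the protocol's constraints harm the patient. Section 9.1 mentions possible interruption as part of treating an adverse event. None of these names a bleed as a trigger.

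**How often.** The documents give no rate for this subset. The nearest evidence is the table in Section 1.3.3, which pools 1071 monotherapy patients:

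- Serious events above 1% are pneumonia, atrial fibrillation, febrile neutropenia and pyrexia. No bleeding term is listed. Since 0.01 × 1071 = 10.7, no single serious bleeding term would then have affected more than 10 patients.
- No bleeding term is listed among grade 3-4 events above 2% either.

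The list is by individual term, comes from B-cell malignancies, and does not capture non-serious CNS bleeds. Several bleeding terms could together exceed 1%. On the other hand, the gap covers only part of serious bleeding: drug-related, grade 1-2, not transfused, no procedure. A range of 0.1% to 1% per patient is therefore assumed.

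With independent patients, P(at least one) = 1 − (1 − p)^n and the expected number is n × p. The values of n are 51 (30 + 21, Section 8.1), 27 (15 + 12, if both cohorts stop after stage 1, Section 8.3) and 56 (planned enrollment with dropouts, Section 8.4, an upper bound for treated patients).

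| Assumed p | n = 27 | n = 51 | n = 56 | Expected cases, n = 51 |
|---|---|---|---|---|
| 0.1% | 2.7% | 5.0% | 5.4% | 0.05 |
| 0.2% | 5.3% | 9.7% | 10.6% | 0.10 |
| 0.5% | 12.7% | 22.6% | 24.5% | 0.26 |
| 1% | 23.8% | 40.1% | 43.0% | 0.51 |

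For example, with p = 1% and n = 51: 1 − 0.99^51 = 1 − 0.599 = 0.401.

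**The case against.** The strongest reply is that the protocol never obliges anyone to dose through a dangerous bleed. Section 5.2 says should, and Table 5-2 is headed as recommended. Sections 5.1 and 5.4 are mandatory once their conditions are judged to be met, and the harm clause in 5.4 overrides a 5.2 default that is bad for the patient. Section 9.2 is a reporting net, and such a net can reasonably be wider than a hold threshold. Serious events are reported within 24 hours, the safety committee meets monthly, and entry criteria exclude recent stroke or intracranial hemorrhage and require platelets of at least 100,000/mm³.

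Much of this stands, and it lowers the weight of the point. What remains is that each of these routes needs an investigator to judge against a specific instruction to continue, and none names a bleed. Reporting and committee review do not set a hold for the patient who is bleeding.

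Three stronger readings are tempting, and the documents do not support them:

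- *Patients are dosed through major hemorrhage in general.* Drug-related bleeds of grade 3 or higher, including all transfused bleeds, are held under 5.2, and bleeds needing a procedure are held under 5.5.
- *An affected patient is close to certain in this trial.* That would need per-patient risks of several percent, and the pooled table in Section 1.3.3 points lower. How many serious or CNS bleeds are graded 1-2 also depends on CTCAE version 4, whose definitions are not reproduced.
- *The CNS gap is established.* A dosing rule in the unseen Section 9.2.2 would close it. The part on serious bleeds outside the CNS would remain.

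**Conclusion.** The point holds in a narrow form. A drug-related grade 1-2 serious bleed, not transfused and needing no procedure under Section 5.5, is major hemorrhage by the protocol's definition and has no required hold. The same applies to a grade 1-2 CNS hemorrhage, subject to what Section 9.2.2 contains. At an assumed 0.1% to 1% per patient, about 0.05 to 0.5 cases would be expected among 51 patients, with a 5% to 40% chance of at least one. The range is an assumption, guided but not fixed by the pooled table in Section 1.3.3. The weight lies in the possible consequence for one patient and not in the number affected. This is a cheap improvement. It does not question the restart dose after a resolved grade 3-4 bleed, call for permanent discontinuation after intracranial hemorrhage, or extend to bleeds judged unrelated to the drug.

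**What to change.** Add to Section 5.2, after the grade 1-2 rule:

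> Exception: for a drug-related grade 1-2 event that meets the Section 9.2.1 definition of major hemorrhage, hold ibrutinib until the patient is clinically stable with no signs of bleeding and the investigator has documented a risk-benefit decision to restart. This hold counts as a toxicity occurrence in Table 5-2. A patient on a temporary hold stays on study and continues scheduled tumor assessments; Table 6-5 footnote b censoring does not apply to the hold.

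The restart standard is the one that Section 5.3 already uses for anticoagulation. The sentence on counting settles the dose at restart. The last sentence is needed because footnote b, read literally, censors anyone who interrupts for an adverse event and moves tumor assessment off trial, which could cost a response assessment. The existing 5.2 rule for bleeds of grade 3 or higher stays unchanged, so those bleeds do not acquire a second restart standard. If Section 9.2.2 exists, check it for a CNS dosing rule first.

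Cost: a protocol amendment, which under Section 13.1 needs approval by the supporting company before it goes to the IRB, and no new assessments. An affected patient loses some dosing time and would be removed if off treatment for more than 3 weeks. One such removal is 1 of 30 carcinoid patients (3.3%) or 1 of 21 pNET patients (4.8%).

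### For a patient already cut to 420 mg for grade 2 toxicity, Section 5.2 and Table 5-2 order a 560 mg restart that Section 5.2 itself forbids, and they disagree on the next step down

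*Combined protocol and SAP*

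**What the plan says.** Section 5.1 sets the starting dose at 560 mg daily, as four 140 mg capsules. Section 5.2 then gives these rules:

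- **No re-escalation.** "Doses of ibrutinib which have been reduced for toxicity may not be re-escalated". No exception is stated.
- **Grade 2 option.** "the investigator may reduce the dose by one level if a grade 2 toxicity persists" and materially affects quality of life. One level down from 560 mg is 420 mg.
- **First qualifying event.** The qualifying drug-related events are non-hematological toxicity at grade 3 or above, neutropenia at grade 3 or above accompanied by fever or infection, and grade 4 hematological events. Drug is held until recovery to grade 1 or better. "Then the drug should be reinitiated at the starting dose".
- **Recurrence.** The dose falls by one capsule (140 mg). A second 140 mg cut may be considered, with a pointer to Table 5-2.
- **Stopping.** "If a patient experiences these drug-related toxicities despite two dose reductions, ibrutinib should be discontinued".

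Table 5-2, introduced as covering these same toxicities, gives absolute doses by occurrence: first "Restart at 560 mg daily", second "Restart at 420 mg daily", third "Restart at 280 mg daily", fourth discontinue.

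**The concern.** The steps in the text are relative to the current dose, while those in the table are absolute and presume a patient who was on 560 mg. The two agree only if nothing else has lowered the dose, yet the grade 2 option is an authorised way to lower it. Nothing in Section 5.2 says what follows for such a patient.

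The stake is dosing safety after a severe toxicity. Read literally, a patient who has just had such an event on 420 mg goes up to 560 mg. At a second event, a site following the table may give no reduction at all. The background sections report major bleeding, some of it fatal (Section 1.3.3.4), and fatal infections (Section 1.3.3.8). Protocol deviations also become hard to judge: at the first event, 560 mg breaks one sentence and 420 mg breaks another.

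**Working it through.** No sample-size or error-rate formula applies. The check applies each written rule event by event.

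**Inputs.** Starting dose 560 mg and capsule size 140 mg (Section 5.1). One-level grade 2 cut, no re-escalation, one-capsule step and stopping after two reductions (Section 5.2). Absolute doses 560, 420, 280 mg, then stop (Table 5-2).

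**Patient with no grade 2 cut (reproduces the table).** Event 1: 560. Event 2: 560 − 140 = 420. Event 3: 420 − 140 = 280. Event 4: two reductions already made, so stop. This matches Table 5-2 exactly.

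**Patient cut to 420 mg before the first event.**

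- Event 1: text and table both give 560 mg. The no-re-escalation ceiling is 420 mg, so the excess is 560 − 420 = 140 mg.
- Event 2, after restarting at 420 mg as the ceiling requires: the text gives 420 − 140 = 280 mg and the table gives 420 mg. The table dose is 420/280 = 1.5 times the text dose. Neither exceeds 420 mg, so the no-re-escalation rule does not choose between them.
- Event 3, if the grade 2 cut counts: the reductions so far are 560 to 420 and 420 to 280, which makes two, so the text stops the drug.
- Event 3, if it does not count: only one reduction has been made, and the text's step gives 280 − 140 = 140 mg. The table gives 280 mg.

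| Route for a patient at 420 mg | Event 1 | Event 2 | Event 3 | Event 4 |
|---|---|---|---|---|
| Text, ceiling obeyed, cut counts | 420 | 280 | stop | – |
| Text, ceiling obeyed, cut does not count | 420 | 280 | 140 | stop |
| Table, first event capped at 420 mg | 420 | 420 | 280 | stop |
| Text, literal 560 mg restart, cut counts | 560 | 420 | stop | – |
| Text, literal 560 mg restart, cut does not count | 560 | 420 | 280 | stop |
| Table, literal | 560 | 420 | 280 | stop |

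After a literal 560 mg restart, text and table agree at event 2. The event 2 conflict therefore appears only when the no-re-escalation rule is obeyed.

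**Patient cut to 420 mg after the first event.** The first event occurs on 560 mg and the restart at 560 mg is correct. A grade 2 cut then takes the dose to 420 mg. At event 2 the text gives 420 − 140 = 280 mg and the table gives 420 mg. The second-event conflict is the same, with no re-escalation involved.

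**The case against.** The strongest reply is that Section 5.2 largely settles itself. The bar on re-escalation is categorical and comes before the steps, so a careful site would restart at 420 mg. At event 2 the text calls for a one-capsule cut, while the table is headed as a recommendation. The sequence needs a persistent grade 2 toxicity, a discretionary cut and then one or two severe events. Drug is held until recovery to grade 1 or better. Removal after more than 3 weeks off drug, investigator discretion (Section 5.4) and a monthly DSMC (Section 13.3.2) all limit exposure.

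Much of this stands, and it bounds the harm. It does not remove the event 1 contradiction, which is explicit in both text and table. At event 2 no rule of precedence between text and table is given.

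Three stronger readings are tempting, and the documents do not support them:

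- *The table always allows one more severe event before stopping.* This holds only if the grade 2 cut counts as a reduction. If it does not, the text route also stops at the fourth event.
- *Sites will work from the table alone.* Section 5.4 does point to Table 5-2, but Sections 1.3.3.3, 1.3.3.5 and 2.1 point to Section 5.2 as a whole.
- *Text and table conflict for everyone.* They agree for every patient with no grade 2 cut.

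**Conclusion.** There is a real internal contradiction in Section 5.2, and it should be corrected. For a patient at 420 mg after a grade 2 cut, the first-event instruction is 140 mg above what the section permits. Once that rule is obeyed, text and table differ by 140 mg at the second event (280 against 420 mg). They differ by the same amount when the cut follows a first event at 560 mg.

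At the third event the outcome may be stopping or 140 mg (text), or 280 mg (table). Which text outcome applies depends on a counting rule that the protocol does not state, so no fixed difference in the number of events before stopping can be claimed.

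This rests on reading Table 5-2 as covering only the qualifying events, as its introduction indicates, so that a grade 2 cut is not itself a table occurrence. The number of patients affected cannot be estimated from the documents and is probably small. The Simon boundaries and power in Section 8.3 are unaffected.

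**What to change.** 1. In Section 5.2, replace the first-event restart sentence with: *The drug should then be restarted at 560 mg, or at the current dose if that has already been reduced for toxicity.*
2. Add a footnote to Table 5-2: *Doses shown apply to patients with no grade 2 dose reduction at any time. If the dose has been reduced for grade 2 toxicity, before or after the first event, restart the first event at the current dose and the second event at 140 mg below the current dose.*

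With these changes, a patient with no grade 2 cut still follows 560, 420, 280 mg, stop. A patient cut before the first event gets 420 then 280 mg. A patient cut between the first and second events gets 560 then 280 mg.

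The sponsor should also decide whether a grade 2 cut counts toward the two reductions, and complete the footnote for the third event accordingly. Either choice is defensible, and these edits do not impose one. Temporary reductions for CYP3A inhibitors (Section 5.3) are not toxicity reductions and are unchanged.

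The cost is one sentence and one footnote in an amendment, with no added patients, visits or procedures. The downside is that a few patients receive 140 mg less than Table 5-2 implies.

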5.2.1 Dose Modification for Hepatic Impaired Subjects

Ibrutinib is metabolized in the liver and therefore subjects with clinically significant hepatic impairment at the time of screening (Child-Pugh class B or C) are excluded from study participation. For subjects who develop mild liver impairment while on study (Child-Pugh class A), the recommended dose reduction for ibrutinib is to a level of 280 mg daily (two capsules). For subjects who develop moderate to severe liver impairment while on study (Child-Pugh class B), the recommended dose reduction is to a level of 140 mg daily (one capsule). Subjects who develop severe hepatic impairment (Child-Pugh class C) must hold study drug until resolved to moderate impairment (Child-Pugh class B) or better. Subjects will be monitored for signs of toxicity and follow dose modification guidance as needed (Refer to Appendix D).

Comment [AT3]: RESPONSE REQUIRED:

Please include the following required dose modification language on hepatic impairment.

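### A drug-related liver event can meet the triggers of both Section 5.2 and Section 5.2.1, and the two sections then conflict with no stated precedence

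*Combined protocol and SAP*

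**What the plan says.** Section 5.2 (Dose Modification) sets its hold rule by toxicity grade: "If a patient experiences a CTCAE grade 3 or higher non-hematological toxicity", or one of two hematological events, and the event is "considered drug-related, ibrutinib should be held until resolution of toxicity to ≤ grade 1. Then the drug should be reinitiated at the starting dose". Table 5-2 gives the dose after the hold by occurrence. The first entry is "Restart at 560 mg daily", followed by 420 mg, 280 mg and discontinuation. For lesser toxicity, patients with drug-related events of "grade 1 or 2 according to CTCAE criteria should continue ibrutinib without dose modification", although the investigator may cut one level for a grade 2 event that persists and weighs on quality of life. The section also says that "Ibrutinib dosing adjustments are to be made according to the greatest degree of toxicity observed", bars re-escalation after a toxicity reduction, and removes patients who are off drug for more than 3 weeks.

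Section 5.2.1 (Dose Modification for Hepatic Impaired Subjects) sets its rule by Child-Pugh class, whatever the cause. Class A arising on study goes to 280 mg. The next rule covers "moderate to severe liver impairment while on study (Child-Pugh class B), the recommended dose reduction is to a level of 140 mg daily". Class C patients "must hold study drug until resolved to moderate impairment (Child-Pugh class B) or better". It closes by sending the reader to the dose modification guidance as needed, without ranking the two sections. Appendix D holds the Child-Pugh score.

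**The concern.** The two sections use different scales, and neither excludes the other. Section 5.2 has no liver exception, and Section 5.2.1 has no exception for drug-related events. Where both apply, a site can follow one written rule and break the other.

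The drug is metabolized in the liver, and inclusion criterion 13 allows for patients with liver metastases, so the overlap is a case the protocol should cover. Safety and tolerability is a secondary objective. If sites resolve the conflict differently, the same patient could receive different doses, and the exposure and safety data would partly reflect which section a site used.

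**Working it through.** No planned figure is at issue, so the check sets the two rules side by side and scores Appendix D.

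**Inputs.** Section 5.2 and Table 5-2: hold rule, grade 1-2 rule, restart at 560, 420 or 280 mg at the first, second or third occurrence. Section 5.2.1: 140 mg in class B, hold in class C. Appendix D: five measures of 1 to 3 points each; 5-6 points is class A, 7-9 is B, 10-15 is C. Bilirubin above 3 mg/dL scores 3. Transaminases are not scored. Class A is left aside: 5 points, the scale minimum, is already class A, so when its rule is triggered is a separate question.

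**Step 1. Can one event meet both triggers?** Points = bilirubin + albumin + INR + ascites + encephalopathy.

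- Bilirubin above 3 mg/dL, other four normal: 3+1+1+1+1 = 7, class B. Bilirubin alone cannot score higher, so it never reaches class C.
- Transaminase rise alone: 1+1+1+1+1 = 5, so no class B conflict arises.

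Whether the class B event is grade 3 or higher depends on CTCAE cut-points, which the protocol cites but does not reproduce. Assume that grade 1 ends at 1.5 x ULN, that grade 3 begins above 3 x ULN, and that ULN is 1.0 to 1.2 mg/dL. Grade 3 then begins above 3 x 1.0 = 3.0 to 3 x 1.2 = 3.6 mg/dL. A bilirubin of 4 mg/dL is grade 3 across that range. A bilirubin of 3.2 mg/dL is grade 3 at ULN 1.0 and grade 2 at ULN 1.2. Both values are class B.

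**Step 2. Class B, patient on 560 mg, first drug-related event.**

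| CTCAE grade | Section 5.2 | Section 5.2.1 |
|---|---|---|
| 1-2 | 560 mg (optional 560 - 140 = 420 mg if grade 2 persists) | 140 mg |
| 3 or higher | no drug until grade 1 or less | 140 mg |

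The rows conflict whichever grade applies, so the assumed cut-points decide only the direction of the conflict. Table 5-2 has no 140 mg step; its lowest is 280 mg.

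**Step 3. Class C, drug-related and grade 3 or higher.** Both sections hold. Section 5.2 resumes at grade 1 or less; Section 5.2.1 ends the hold at class B or better. The 3-week limit makes this matter: a patient back in class B within 3 weeks but still above grade 1 may resume under one section and heads for removal under the other. The written doses also differ: 560, 420 or 280 mg by occurrence under Table 5-2, against 140 mg while in class B.

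**Step 4. Is there a fourfold difference at restart?** The written doses give 560/140 = 4 at a first occurrence, but they may apply at different times. For an isolated bilirubin rise on the assumed cut-points, grade 1 means at most 1.5 x 1.0 = 1.5 to 1.5 x 1.2 = 1.8 mg/dL. That is below 2 mg/dL and scores 1, for a total of 5. The patient has left class B by the time Section 5.2 permits restart, so 140 mg is no longer the comparison.

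**Step 5. Re-escalation.** If a Section 5.2.1 cut to 140 mg counts as a reduction for toxicity, the bar in Section 5.2 rules out a later Table 5-2 restart at 280 mg or more. If it does not count, that restart is open. The text does not say.

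**The case against.** The strongest reply is that the sections can be layered. Section 5.2.1 sits inside Section 5.2 and has a different purpose, exposure in an impaired liver. It calls its class A and B doses recommended, uses mandatory wording only for class C, and never waives a toxicity hold. With the sentence on the greatest degree of toxicity, a reader could hold under Section 5.2 at grade 3 or higher and let Section 5.2.1 set the dose by liver function.

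That reading is available, but the protocol does not state it and it leaves gaps. The greatest-degree sentence ranks severity, not sections; at most it favors a hold, and it sets no resume point or restart dose. The word *recommended* does not rank Section 5.2.1 lower, because Table 5-2 carries the same word in its title. Layering also does not settle a class B event of grade 1-2, where Section 5.2 keeps the dose and Section 5.2.1 cuts it.

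Two limits stand. Impairment from progressing liver metastases is not drug-related, so it falls under Section 5.2.1 without triggering the Section 5.2 rules. Frequency is also unknown: Section 1.3.3 lists no hepatic event among the frequent or named risks, and Child-Pugh B and C are excluded at entry.

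**Conclusion.** The concern holds for drug-related liver events that reach Child-Pugh B or C. In class B the current-dose instructions are incompatible at every CTCAE grade. In class C the immediate instruction agrees, but the resume point and the dose at resumption do not. The status of Section 5.2.1 reductions under the re-escalation bar is undefined. That a particular class B event is grade 3 or higher is an assumption; that some conflict exists in class B is not.

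A reader might infer more than the documents support:

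- That every drug-related liver toxicity falls under both rules. Isolated transaminase rises do not create the class B conflict.
- That the sections give opposite orders throughout. In class C both hold.
- That patients would be restarted at four times the hepatic dose. The 560 mg step is for a first occurrence only, and the contrast is not shown for an isolated bilirubin rise that has returned to grade 1. It would need a patient still in class B through another measure once the toxicity itself had resolved.

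This is a contradiction between written safety instructions that should be corrected. It does not enter the sample size, power or type 1 error.

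**What to change.** Reconcile Sections 5.2 and 5.2.1. For a liver event that meets both triggers, state which section governs (a) the hold, (b) the point of resumption and (c) the restart dose, including how that dose relates to the occurrence steps in Table 5-2. State also whether the bar on re-escalation applies to Section 5.2.1 reductions. The sponsor and investigator decide the clinical content; this point takes no view on which dose or rule is right.

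As an editorial matter, keep the word *severe* for one Child-Pugh class. Section 5.2.1 now attaches it to both B and C, although the class in brackets makes the meaning recoverable.

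The cost is a text amendment to the two sections, with the drug supplier's review and IRB submission under Section 13.1. It needs no new tests or visits and no change to the statistical design. The clinical decision behind the wording takes more than one added sentence, since three items and the re-escalation question must be settled.
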